18.10 Institutional Review Board/Ethics Committee

The PI will assure that an appropriately constituted IRB/EC that complies with the requirements of 21 CFR Section 56 or written assurance of compliance with ICH (E6) guidelines will be responsible for the initial and continuing review and approval of the clinical study. Before initiation of the study, the PI or designee will forward copies of the protocol and Consent Form to be used for the study to the IRB/EC for its review and approval.

The PI or designee will also assure that all changes in the research activity and all unanticipated problems involving risks to human subjects or others will be reported promptly to the IRB/EC, and that no changes will be made to the protocol without prior Sponsor and IRB/EC approval, except where necessary to eliminate apparent immediate hazards to human subjects.

The Investigator or designee will be responsible for submitting periodic progress reports to the IRB/EC at intervals appropriate to the degree of subject risk involved in the study, but not less than once per year and at the completion or termination of the study.

18.11 Subject Privacy

The Investigators affirm and uphold the principle of the subject's right to privacy. The Investigators shall comply with applicable national and local privacy laws.

20.0 APPENDICES

Appendix A: ECOG Performance Status Scale

Appendix B: Study Calendar

Appendix C: Location of Acupuncture and Acupressure Points

Appendix D: EORTC QLQ CIPN-20

Appendix E: NCI PRO-CTCAE

Appendix F: Brief pain inventory

Appendix G: Oral symptoms questionnaire

Appendix H: Neuropen Assessment Points

Appendix I: Tuning Fork Assessment Points

Appendix J: Acupressure Diary

Appendix K: Acupuncture Expectancy Scale

Appendix L: Acupressure Ear Seed Care Instructions

Appendix M: Waitlist Acupuncture Voucher

Appendix N: Research Acupuncture Appointments in the Wellness Clinic

Appendix O: Cryotherapy Phone Script

Appendix P: Cryotherapy Questionnaire

20.1 APPENDIX A: ECOG Performance Status Scale**ECOG Performance Status Scale**

| GRADE | SCALE |
|-------|--|
| 0 | Fully active, able to carry out all pre-disease performance without restriction |
| 1 | Restricted in physically strenuous activity but ambulatory and able to carry out work of a light or sedentary nature, e.g., light housework, office work |
| 2 | Ambulatory and capable of all self-care but unable to carry out work activities. Up and about more than 50% of waking hours. |
| 3 | Capable of only limited self-care, confined to bed or chair more than 50% of waking hours. |
| 4 | Completely disabled. Cannot carry on any self-care. Totally confined to bed or chair. |
| 5 | Dead |

20.2 APPENDIX B: Study Calendar

Study Calendar

| Procedure | Screening within 14 days | Cycle 1 | | Cycles 2-3 ⁶ | | Cycle 4 ⁶ | | | Cycles 5-6 ⁶ | | End of Tx ⁷ | Waitlist control visit ⁸ |
|-------------------------------------|--------------------------|----------------|----------------|-------------------------|----------------|----------------------|----------------|----------------|-------------------------|----------------|------------------------|-------------------------------------|
| | | Day 1 | Day 3 | Day 1 | Day 3 | Day 1 | Day 3 | Day 8 ± 2 days | Day 1 | Day 3 | | |
| Physical Exam ¹ | X | X | | X | | X | | | X | | X | X |
| Medical History | X | X | | X | | X | | | X | | X | |
| Pregnancy Test | X | | | | | | | | | | | |
| CBC ² | X | X | | X | | X | | | X | | | |
| Oxaliplatin-based chemotherapy | | X | | X | | X | | | X | | | |
| Acupuncture treatment | | X ³ | X ³ | X ³ | X ³ | X ³ | X ³ | | X ³ | X ³ | | X |
| Acupressure training ^{3,4} | | X | | X | X | | | | | | | |
| Acupressure diary review | | | | X | | X | | | X | | X | |
| Cryotherapy | | X | | X | | X | | | X | | | |
| AE Assessment | | X | | X | | X | | | X | | X | X ⁹ |
| PROs ⁵ | | X | | | | X | | X ⁵ | | | X | |
| Neuropen, tuning fork | | X | | | | X | | | | | X | |
| Acupuncture Expectancy Scale | X | | | | | | | | | | | |

¹ On day 3, only vital signs are needed (a complete physical exam is not required). For waitlist control visits, this will include notation of pulse, tongue color, and any other findings considered notable to the acupuncturist

² Labs may be obtained up to 3 days prior. If lab values are below the accepted treatment thresholds, they must be repeated and above treatment parameters before treatment delivery.

³ Patients in Arm A (intervention arm) only

⁴ Acupressure retraining will be completed at the cycle 2, day 1 visit if a patient has completed <50% of the prescribed regimen

⁵ PROs for all time points: EORTC QLQ CIPN-20, NCI-PRO CTCAE, BPI, oral symptoms. At C4D8, a sub-set of the PROs will be re-administered: EORTC QLQ CIPN-20, NCI-PRO CTCAE, BPI

⁶ Study procedures will be timed with patient chemotherapy. If chemotherapy is delayed, then the acupuncture, acupressure, and standard-of-care treatments will be delayed accordingly.

[figure not shown]
⁷ See section 9.9 for a description of the permitted time range for the EOT visit.

⁸ Patients in Arm B (control arm) only

[figure not shown]
⁹ Limited AE assessment of acupuncture-associated toxicities (bruising, bleeding, pain, other) will be assessed, as well as chief complaint, and any other major considerations for the acupuncturist.

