9.1 Treatment Plan Overview

9.2 Acupuncture and Acupressure Intervention

The intervention group will receive acupuncture during chemotherapy infusion (day 1) and 5-FU pump disconnect (day 3) of each biweekly chemotherapy infusion x6 cycles (*i.e.* 12 acupuncture treatments over 12 weeks). Acupuncture treatments will be specifically targeted to prevent, treat, or mitigate neuropathy symptoms, pain, fatigue, nausea and anxiety. Patients will receive 30-minute acupuncture treatments in the seated or supine position. Standard acupoint techniques for point location²² will be utilized and Clean Needle Technique²³ will be followed using 32-40-gauge x 30-40mm Seirin acupuncture needles.

On day 1 the acupuncture points will be needled bilaterally at: ST36, SP6, LI10, GB40, P6, auricular shen men, and on the midline at Yin Tang (EX-HN3) and GV20. On day 3 the acupuncture points will be needled bilaterally at: LI4, LR3, ST36, SP6, LI10, GB40, P6, auricular shen men, and on the midline at Yin Tang (EX-HN3) and GV20. For patients unable to tolerate peripheral cryotherapy, the day 3 acupuncture protocol will be administered on day 1.

After the initial acupuncture treatment, the study acupuncturist will instruct the patient on how to locate and self-administer acupressure for key acupoints: bilateral LI4 (for pain, oral dysesthesia), bilateral P6 (nausea), and midline GV20 (fatigue). These acupoints are based on previously published studies,¹²⁻¹⁵ Traditional Chinese Medicine (TCM) theory,²² and current understanding of innervation and neuromodulation of acupoints.¹³ Auricular shen men points (anxiety) will be stimulated with vaccaria seeds applied by the acupuncturists on day 3 and removed after 4 days (day 7 of the cycle). Patients will be taught to self-administer an 11-minute acupressure regimen daily by stimulating each acupoint in a circular motion for 2 minutes on each bilateral points of LI4 and P6, 2 minutes on midline GV20, and to gently press the ear seeds on shen men for 30 seconds three times per day. The acupuncturists will provide additional teaching during the acupressure training on Cycle 1 Day 1 instructing the patients to utilize auricular Shen Men point during cryotherapy to help mitigate possible unpleasant effects of cryotherapy including: headache, toothache, and/or cold aversion/pain.

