9.4 Waitlist Control

To increase participant willingness to be randomized and to increase trial retention, participants randomized to the control arm will receive coupons for six acupuncture treatments at SCCA South Lake Union clinic to be used any time after completion of the individual's duration (approximately 12 weeks) on the study (Appendices M and N). At the time of these visits, AEs and limited exam findings may be collection, which will be entered into the database as well. These visits will ideally be during or coordinated with standard-of-care visits. However, if patients have completed treatment, they may attend acupuncture-only visits.

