9.9 End of Treatment (EOT) Visit Schedule and Procedures

The EOT visits for all subjects who discontinue from the study should ideally occur 14 days after day 1 of the prior cycle of chemotherapy (which would be 11 days from the last acupuncture treatment). The EOT visit is permitted in the range of 7-30 days after the last use of (Arm A) acupuncture treatment or (Arm B) cryotherapy use but must occur prior to beginning another treatment or receiving another dose of chemotherapy. Procedures to be performed during the EOT Visit include:

- Physical Exam
- Administration of the final QOL measures
- Vital Signs
- Performance Status
- AE Assessment
- Concomitant Medication

As per 6.7. patients who are on the waitlist control arm and choose to use their acupuncture coupons will have the optional EOT visit for uniform data collection, but will also have limited data collected at the time of each acupuncture session to note any toxicities or major symptoms at the time of those visit.

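### No AE assessment is scheduled at any Arm A Day 3 acupuncture session, and the named needling toxicities are solicited only at the waitlist visits

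*Combined protocol and SAP*

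**What the plan says.** **Arm A sessions.** Section 9.2 plans "12 acupuncture treatments over 12 weeks", on the infusion day (Day 1) and the pump-disconnect day (Day 3) of six biweekly cycles. Day 3 has the larger point set: "On day 3 the acupuncture points will be needled bilaterally at: LI4, LR3, ST36, SP6, LI10, GB40, P6, auricular shen men", plus two midline points. LI4 and LR3 are not in the usual Day 1 set. The ear seeds are also applied on Day 3.

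**Arm A AE schedule.** Appendix B marks acupuncture on Day 1 and Day 3 of every cycle. Up to the end-of-treatment column, its AE row reads "AE Assessment | | X | | X | | X | | | X | | X". The marks fall on Day 1 of every cycle and at end of treatment; every Day 3 cell is blank, and so is cycle 4 Day 8. Footnote 1, attached to the physical exam row, adds: "On day 3, only vital signs are needed (a complete physical exam is not required").

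**Waitlist visits (Arm B).** The last calendar column carries footnote 9: "Limited AE assessment of acupuncture-associated toxicities (bruising, bleeding, pain, other) will be assessed". Section 9.9 says that these patients "will also have limited data collected at the time of each acupuncture session to note any toxicities or major symptoms". Section 9.4 is only permissive: "AEs and limited exam findings may be collection, which will be entered into the database as well".

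**General duty.** Sections 13.4, 13.5 and 13.7 require every AE to be assessed, graded by CTCAE version 5.0 and recorded from first acupuncture exposure. They do not limit this to calendar visits, but they schedule no contact either.

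**The concern.** The plan treats a short, solicited check for needling effects as worth doing at each optional session after the trial period. It schedules no such check at half of the sessions of the intervention under test, and those are the sessions with more needling.

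Bruising, minor bleeding and needling pain are brief. Section 13.4 asks for start date, stop date, grade and relatedness, and section 13.6 bases attribution partly on temporal sequence. For an event that has resolved before anyone asks, those fields rest on memory, or the event is never recorded. Entry allows platelet counts just above 20 thousand/microL (section 7.1.3), so bleeding and bruising are relevant events here. What is at stake is how complete the acupuncture safety record is; the primary endpoint is not affected.

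**Working it through.** **Session count (the plan's own figure).** 6 cycles x 2 days = 12 sessions per Arm A patient, as section 9.2 states. With 28 patients (section 6.4), 28 x 12 = 336 planned sessions.

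**Same-visit AE coverage, from Appendix B.**
- Day 1 marks: cycle 1 (1) + cycles 2-3 (2) + cycle 4 (1) + cycles 5-6 (2) = 6. Adding end of treatment gives 7 scheduled assessments.
- Arm A sessions with an AE mark on the day: 6 of 12 (50%).
- Arm A sessions without one: 6 of 12, all on Day 3; 28 x 6 = 168 of 336.
- Waitlist sessions: up to 6, all with a limited check if footnote 9 and section 9.9 are followed.

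**Needling on unassessed days, from section 9.2.**
- Day 1: 6 bilateral + 2 midline points = 14 insertions.
- Day 3: 8 bilateral + 2 midline points = 18 insertions.
- Per patient: 6 x 14 = 84 and 6 x 18 = 108, total 192. The share on Day 3 is 108/192 = 56%. It is 50% for a patient given the Day 3 set on both days, which section 9.2 provides for when peripheral cryotherapy is not tolerated.

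**Time to the next scheduled enquiry.**
- After Day 3 of an undelayed 14-day cycle: Day 15 - Day 3 = 12 days, and longer if chemotherapy is delayed.
- After the last session: section 9.9 gives an ideal of 11 days and permits 7 to 30.
- Ear seeds come off on Day 7 (section 9.2, Appendix L), or on Day 8 according to the Appendix J diary. The wearing period therefore ends 8 or 7 days before the next Day 1.

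**Effect of adding a check at each Day 3 session.**
- Same-visit coverage rises from 6 of 12 to 12 of 12, and scheduled assessments from 7 to 13.
- Effects of Day 1 needling that appear after that visit's enquiry would be asked about 2 days later (Day 3 - Day 1) instead of 14 (Day 15 - Day 1).
- The 12-day interval after Day 3 and the 7 to 30 days after the last session do not change.

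**The case against.** The strongest reply is that Arm A is well covered overall. It has 7 unrestricted assessments, and the calendar puts a physical exam and medical history at the same visits. The waitlist has at most 6 assessments, each described as limited. Footnote 9 can be read as a reduction for optional visits, and bruising or bleeding falls within the Arm A assessments anyway. This stands: a reader might infer that the tested intervention is monitored less closely overall, and the documents do not support that. The shortfall concerns only solicited enquiry at the session.

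Other points that stand in whole or part:
- **The calendar is not exhaustive.** Footnote 1 calls for Day 3 vital signs although no Day 3 cell of its row is marked, so a blank cell is not proof that nobody asks. Still, no other section schedules a Day 3 AE enquiry.
- **Other contacts exist.** The cycle 4 Day 8 questionnaires ask about pain, and the acupressure diary has a comments column that is reviewed on Day 1 from cycle 2. Neither asks about bruising or bleeding.
- **Blood counts are repeated.** The CBC is scheduled on Day 1 of each cycle, and footnote 2 requires values below treatment thresholds to recover before treatment. The entry limits therefore do not describe counts throughout; equally, no CBC is scheduled on Day 3.
- **Waitlist wording.** Section 9.4 is permissive, so a check at every waitlist session is not uniformly required.

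Three further inferences are tempting and should not be drawn:
- **That the toxicity discontinuation rule could not be applied promptly.** In section 11.0 it covers only Grade 4 or life-threatening events. Nothing suggests that recognising one depends on a Day 3 calendar mark.
- **That Arm A would show lower AE rates than the waitlist sessions.** Section 16.5 plans no such comparison.
- **That a Day 3 check closes the interval after Day 3, or detects reactions to seeds applied that day.** It does neither.

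**Conclusion.** The point holds as a gap in scheduled, solicited safety enquiry: 6 of 12 Arm A sessions per patient (168 of 336 planned) have no AE assessment on the day, and the named needling toxicities are solicited only in Arm B. Day 3 events are not excluded from capture. Short-lived ones depend on spontaneous report, or on recall about 12 days later or at end of treatment. Under-recording is therefore a risk and not a certainty; serious events would probably surface on their own.

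The counts assume full attendance, undelayed 14-day cycles and Appendix B taken as written. The documents do not say whether the Day 1 assessment comes before or after needling, so Day 1 coverage means same-visit coverage only. No endpoint definition, power or sample size figure is affected. The change is worth making because it is cheap, not because the trial's conclusions depend on it.

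**What to change.** - **Appendix B:** extend the limited check in footnote 9 to every Arm A acupuncture visit, Days 1 and 3. The acupuncturist completes it after needle removal and also asks about effects since the previous session. On Day 1 that includes reactions to the previous cycle's ear seeds.
- **Section 16.5:** state that the CTCAE assessments on Day 1 and at end of treatment are the only CTCAE source for between-arm comparisons. Pain is among the incidences compared, so needling pain picked up at extra Arm A contacts could otherwise enter that comparison on one side only.
- **Sections 9.4 and 9.9 and footnote 9:** reconcile the permissive wording in 9.4 with the definite wording in the other two.

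The cost is a calendar edit and reuse of the waitlist items, a minute or two at visits that already take place with the acupuncturist present. It needs no new visit or staff. The downside is that more minor needling events will be recorded in Arm A, and the report should say that they were solicited.

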20.3 APPENDIX C: Location of Acupuncture and Acupressure Points

[figure not shown]
Location of acupuncture points. All points needled bilaterally (except midline points)
Day 1 Acupuncture Protocol

Day 3 Acupuncture Protocol

Location of acupressure points. All points pressured bilaterally (except midline GV20)

20.4 APPENDIX D: EORTC QLQ CIPN-20

| EORTC QLQ – CIPN20 | | | | |
|---|---------------------------|---------------------|------------------------|----------------------|
| Patients sometimes report that they have the following symptoms or problems. Please indicate the extent to which you have experienced these symptoms or problems during the past week. Please answer by circling the number that best applies to you. | | | | |
| | Not at all | A little | Quite a bit | Very much |
| During the past week | | | | |
| 1. Did you have tingling fingers or hands? | 1 | 2 | 3 | 4 |
| 2. Did you have tingling toes or feet? | 1 | 2 | 3 | 4 |
| 3. Did you have numbness in your fingers or hands? | 1 | 2 | 3 | 4 |
| 4. Did you have numbness in your toes or feet? | 1 | 2 | 3 | 4 |
| 5. Did you have shooting or burning pain in your fingers or hands? | 1 | 2 | 3 | 4 |
| 6. Did you have shooting or burning pain in your toes or feet? | 1 | 2 | 3 | 4 |
| 7. Did you have cramps in your hands? | 1 | 2 | 3 | 4 |
| 8. Did you have cramps in your feet? | 1 | 2 | 3 | 4 |
| 9. Did you have problems standing or walking because of difficulty feeling the ground under your feet? | 1 | 2 | 3 | 4 |
| 10. Did you have difficulty distinguishing between hot and cold water? | 1 | 2 | 3 | 4 |
| 11. Did you have a problem holding a pen, which made writing difficult? | 1 | 2 | 3 | 4 |
| 12. Did you have difficulty manipulating small objects with your fingers (for example, fastening small buttons)? | 1 | 2 | 3 | 4 |

| | | | | |
|--|---|---|---|---|
| 13. Did you have difficulty opening a jar or bottle because of weakness in your hands? | 1 | 2 | 3 | 4 |
| During the past week | | | | |
| 14. Did you have difficulty walking because your feet dropped downwards? | 1 | 2 | 3 | 4 |
| 15. Did you have difficulty climbing stairs or getting up out of a chair because of weakness in your legs? | 1 | 2 | 3 | 4 |
| 16. Were you dizzy when standing up from a sitting or lying position? | 1 | 2 | 3 | 4 |
| 17. Did you have blurred vision? | 1 | 2 | 3 | 4 |
| 18. Did you have difficulty hearing? | 1 | 2 | 3 | 4 |
| Please answer the following question only if you drive a car | | | | |
| 19. Did you have difficulty using the pedals? | 1 | 2 | 3 | 4 |
| Please answer the following question only if you are a man | | | | |
| 20. Did you have difficulty getting or maintaining an erection? | 1 | 2 | 3 | 4 |

20.5 APPENDIX E: NCI PRO-CTCAE
NCI PRO-CTCAE

As individuals go through treatment for their cancer they sometimes experience different symptoms and side effects. For each question, please select the one response that best describes your experiences over the past 7 days...

| | | | | | |
|--|--|------------------------------|------------------------------------|----------------------------------|---|
| 1. | In the last 7 days, how OFTEN did you have NAUSEA? | | | | |
| |  Never |  Rarely |  Occasionally |  Frequently |  Almost constantly |
| In the last 7 days, what was the SEVERITY of your NAUSEA at its WORST? | | | | | |
| |  None |  Mild |  Moderate |  Severe |  Very severe |

| | | | | | |
|--|--|------------------------------|------------------------------------|----------------------------------|---|
| 2. | In the last 7 days, how OFTEN did you have VOMITING? | | | | |
| |  Never |  Rarely |  Occasionally |  Frequently |  Almost constantly |
| In the last 7 days, what was the SEVERITY of your VOMITING at its WORST? | | | | | |
| |  None |  Mild |  Moderate |  Severe |  Very severe |

| | | | | | |
|--|--|------------------------------------|--------------------------------|-----------------------------------|-----------------------------------|
| 3. | In the last 7 days, what was the SEVERITY of your NUMBNESS OR TINGLING IN YOUR HANDS OR FEET at its WORST? | | | | |
| |  None |  Mild |  Moderate |  Severe |  Very severe |
| In the last 7 days, how much did NUMBNESS OR TINGLING IN YOUR HANDS OR FEET INTERFERE with your usual or daily activities? | | | | | |
| |  Not at all |  A little bit |  Somewhat |  Quite a bit |  Very much |

| | | | | | |
|--|--|------------------------------------|------------------------------------|-----------------------------------|---|
| 4. | In the last 7 days, how OFTEN did you have PAIN? | | | | |
| |  Never |  Rarely |  Occasionally |  Frequently |  Almost constantly |
| In the last 7 days, what was the SEVERITY of your PAIN at its WORST? | | | | | |
| |  None |  Mild |  Moderate |  Severe |  Very severe |
| In the last 7 days, how much did PAIN INTERFERE with your usual or daily activities? | | | | | |
| |  Not at all |  A little bit |  Somewhat |  Quite a bit |  Very much |

| | | | | | |
|--|--|--------------------------------|-----------------------------------|---------------------------------|-----------------------------------|
| 5. | In the last 7 days, what was the SEVERITY of your INSOMNIA (INCLUDING DIFFICULTY FALLING ASLEEP, STAYING ASLEEP, OR WAKING UP EARLY) at its WORST? | | | | |
| |  None |  Mild |  Moderate |  Severe |  Very severe |
| In the last 7 days, how much did INSOMNIA (INCLUDING DIFFICULTY FALLING ASLEEP, STAYING ASLEEP, OR WAKING UP EARLY) INTERFERE with your usual or daily activities? | | | | | |
|  Not at all |  A little bit |  Somewhat |  Quite a bit |  Very much | |

| | | | | | |
|---|---|--------------------------------|-----------------------------------|---------------------------------|-----------------------------------|
| 6. | In the last 7 days, what was the SEVERITY of your FATIGUE, TIREDNESS, OR LACK OF ENERGY at its WORST? | | | | |
| |  None |  Mild |  Moderate |  Severe |  Very severe |
| In the last 7 days, how much did FATIGUE, TIREDNESS, OR LACK OF ENERGY INTERFERE with your usual or daily activities? | | | | | |
|  Not at all |  A little bit |  Somewhat |  Quite a bit |  Very much | |

| | | | | | |
|---|---|--------------------------------|------------------------------------|-----------------------------------|---|
| 7. | In the last 7 days, how OFTEN did you feel ANXIETY? | | | | |
| |  Never |  Rarely |  Occasionally |  Frequently |  Almost constantly |
| In the last 7 days, what was the SEVERITY of your ANXIETY at its WORST? | | | | | |
|  None |  Mild |  Moderate |  Severe |  Very severe | |
| In the last 7 days, how much did ANXIETY INTERFERE with your usual or daily activities? | | | | | |
|  Not at all |  A little bit |  Somewhat |  Quite a bit |  Very much | |

| | | | | | |
|---|---|--------------------------------|------------------------------------|-----------------------------------|---|
| 8. | In the last 7 days, how OFTEN did you FEEL THAT NOTHING COULD CHEER YOU UP? | | | | |
| |  Never |  Rarely |  Occasionally |  Frequently |  Almost constantly |
| In the last 7 days, what was the SEVERITY of your FEELINGS THAT NOTHING COULD CHEER YOU UP at their WORST? | | | | | |
|  None |  Mild |  Moderate |  Severe |  Very severe | |
| In the last 7 days, how much did FEELING THAT NOTHING COULD CHEER YOU UP INTERFERE with your usual or daily activities? | | | | | |
|  Not at all |  A little bit |  Somewhat |  Quite a bit |  Very much | |

| | | | | | |
|---|---|--------------------------------|------------------------------------|-----------------------------------|---|
| 9. | In the last 7 days, how OFTEN did you have SAD OR UNHAPPY FEELINGS? | | | | |
| |  Never |  Rarely |  Occasionally |  Frequently |  Almost constantly |
| In the last 7 days, what was the SEVERITY of your SAD OR UNHAPPY FEELINGS at their WORST? | | | | | |
|  None |  Mild |  Moderate |  Severe |  Very severe | |
| In the last 7 days, how much did SAD OR UNHAPPY FEELINGS INTERFERE with your usual or daily activities? | | | | | |
|  Not at all |  A little bit |  Somewhat |  Quite a bit |  Very much | |

